8.5.3 Rescue therapy

The following rescue therapy options will be provided as needed for subject safety. Even if rescue therapies are performed, the subject can continue in the study unless investigators/subinvestigators determine study withdrawal is appropriate. Details of any rescue therapy implemented will be recorded in the subject's CRF.

(1) ESA formulations

If a subject has received maximum dosages of MT-6548 Tablets for ≥ 2 weeks and meets all criteria below, the investigator/subinvestigator may administer an ESA as a rescue therapy to improve Hb levels if necessary in order to secure subject safety. An ESA-based rescue therapy may also be provided without meeting the criteria below if the investigator/subinvestigator considers it necessary to secure subject safety, such as in cases of acute decreases in Hb levels. Administration of MT-6548 Tablets will be discontinued when an ESA-based rescue therapy is provided. Administration of MT-6548 Tablets may be resumed after an improvement in Hb levels and should not be coadministered with a rescue therapy with an ESA. Subjects who are not expected to resume administration of MT-6548 Tablets will be withdrawn from the study.

- ✓ Anaemia or anaemia symptoms (e.g., fatigue, weakness, shortness of breath, chest pain, confusion, dizziness) become aggravated compared to the first day of the treatment period to the point they are clinically problematic.
- ✓ Hb levels drop to < 8.0 g/dL.

(2) RBC transfusion

Usually, RBC transfusions are performed when clinically necessary in instances of acute or major bleeding. For less severe anemia, which may be exacerbated, or moderate to severe anemia symptoms, RBC transfusions may be performed as needed clinically at the discretion of the investigator/subinvestigator.

(3) Phlebotomy

Phlebotomy may be performed at investigator/subinvestigator discretion in cases of hyperviscosity syndrome, if the rate of Hb increase is concerning to investigators/subinvestigators, or if Hb levels are high enough to warrant concern to investigators/subinvestigators.

Rationale

Set out of consideration for subject safety.

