Table number	Contents																																																								
Table 14.1.1.1	Analysis Sets and Disposition (Subjects enrolled in Treatment Period)																																																								
Table 14.1.2.1	Primary Reason for Discontinuation (Subjects enrolled in Treatment Period)																																																								
Table 14.1.2.2	Reasons for Interruption of Study Drug (Subjects enrolled in Treatment Period)																																																								
Table 14.1.3.1.1	Demographics and Baseline Characteristics (FAS)																																																								
Table 14.1.3.2.1	Demographics and Baseline Characteristics (Safety Analysis Set)																																																								
Table 14.1.4.1.1	Treatment Compliance (FAS)																																																								
Table 14.1.4.2.1	Treatment Compliance (Safety Analysis Set)																																																								
Table 14.1.4.3.1	Duration of Exposure to Study Drug (FAS)																																																								
Table 14.1.4.4.1	Duration of Exposure to Study Drug (Safety Analysis Set)																																																								
Table 14.1.4.5.1	Cumulative Dose of Study Drug (FAS)																																																								
Table 14.1.4.5.2	Cumulative Dose of Study Drug (Safety Analysis Set)																																																								
Table 14.2.1.1.1	Hb: Average of Week 20 and Week 24 (LOCF, FAS)																																																								
Table 14.2.1.2.1	Hb: Average of Week 20 and Week 24 by MMRM (FAS)																																																								
Table 14.2.2.1.1	Hb: Absolute and Change from Baseline (FAS)																																																								
Table 14.2.2.2.1	Hb: Absolute by MMRM (FAS)																																																								
Table 14.2.2.3.1	Hb: Change from Baseline by MMRM (FAS)																																																								
Table 14.2.2.4.1	Hb: Proportion of Subjects with Hb within Target Range ( $10 \leq$ to $<12$ g/dL) (FAS)																																																								
Table 14.2.2.5.1	Hb: Time to Reach Target Hb Range ( $10 \leq$ to $<12$ g/dL) (FAS)																																																								
Table 14.2.2.6.1.1	Hb: Rate of Increase from baseline to Week 4 and Week 6 (FAS)																																																								

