### **6.3 Handling of efficacy endpoints if rescue therapy is performed**

If rescue therapy is performed, data from the day after rescue therapy should not be used to assess efficacy.

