#### 7.1.2 Descriptive statistics to calculate

Types of descriptive statistics to be calculated for each variable are provided below.

Number of subjects, mean, standard deviation (SD), median, minimum, maximum, and 2-sided 95% CI of the mean

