## 7.5 Efficacy analysis

As a general rule, efficacy analysis will be performed on the FAS. When necessary, descriptive statistics for continuous variables should be calculated and frequency and proportion will be calculated for discrete variables. No data from the day after the rescue therapy implementation date should be included in the efficacy analysis.

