The time course diagram should be prepared for mean Hb values at each evaluation time point in the treatment period. 95% CI of the mean will be represented by an error bar. The time course diagram should be prepared for Hb values at each evaluation time point of the treatment period in each subject.

(3) Proportion of subjects with mean Hb levels within the target range (10.0–12.0 g/dL), <10.0 g/dL, and ≥12.0 g/dL at each time point of the treatment period

The number, proportion, and 95% CI (Clopper-Pearson [Exact] method) of the proportion of subjects with Hb value within the target range (10.0 to <12.0 g/dL, within), <10.0 g/dL (below), and ≥12.0 g/dL (above) at each time point of the treatment period should be provided. Before and after comparison should be conducted for changes from the first day of the treatment period to each evaluation time point using the McNemar test.

The proportion of subjects in each Hb category (within the target range [10.0 to <12.0 g/dL], <10.0 g/dL, and ≥12.0 g/dL) at each evaluation time point of the treatment period should be provided as a stacked bar graph assuming that the number of subjects at each evaluation time point is 100%. Stacked bar charts should be separately prepared.

(4) Number of days from the first day of the treatment period required to reach the target Hb range (10.0 g/dL to <12.0 g/dL)

Descriptive statistics should be calculated for number of days required from the first day of the treatment period to reach target Hb range (10.0 g/dL to <12.0 g/dL). The number of days should be calculated as the first evaluation date reached target Hb range – first date of the treatment period

+ 1. If target Hb range is not reached, the final date of evaluations – first date of the treatment period + 1 should be assumed.

A Kaplan-Meier plot should be shown for days from the first day of the treatment period required to reach the target Hb range.

No subjects with an Hb value of  $\geq 10.0$  g/dL on the first day of the treatment period will be included in the calculation.

(5) Hb value increase rate

Descriptive statistics should be calculated for the Hb value increase rate (g/dL/week).

The Hb value increase rate should be analyzed by 2 methods defined in the “Hb value increase rate”.

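### SAP 7.5.1(4) counts the last evaluation day of subjects who never reach target Hb as their days to target, so the reported mean, SD and 95% CI do not describe time to target

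*SAP*

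**What the plan says.** Time to target is item (4) of the five listed under the primary endpoint (SAP 3.1.1; Protocol 5.3.1). SAP 7.5.1(4) opens with "Descriptive statistics should be calculated for number of days required from the first day of the treatment period to reach target Hb range". A reacher's value is the first date in range minus the first treatment date, plus 1. For the rest the text continues "If target Hb range is not reached, the final date of evaluations", again minus the first treatment date plus 1, and says this is to be assumed.

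SAP 7.1.2 defines descriptive statistics as "Number of subjects, mean, standard deviation (SD), median, minimum, maximum, and 2-sided 95% CI of the mean". Elsewhere the SAP waives the CI where it is not wanted (for example 7.3, 7.4 and 7.6.2); 7.5.1(4) has no waiver. The only exclusion is first-day Hb of 10.0 g/dL or more. In the errata's list of output tables, Table 14.2.2.5.1 is titled "Hb: Time to Reach Target Hb Range".

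The next instruction is "A Kaplan-Meier plot should be shown for days from the first day of the treatment period required to reach the target Hb range". No event, censoring rule, Kaplan-Meier median or number reaching target is specified for this item. Protocol 13.3.2 orders the same two outputs and has no rule for non-reachers. SAP section 9 does not list this rule as a change from the protocol.

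On rescue, Protocol 8.5.3 says "Even if rescue therapies are performed, the subject can continue in the study", while SAP 6.3 says "If rescue therapy is performed, data from the day after rescue therapy should not be used to assess efficacy" and SAP 7.5 says "No data from the day after the rescue therapy implementation date should be included in the efficacy analysis".

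**The concern.** A subject last evaluated without success on a given day has a time to target known only to exceed that day. Entering the day as if it were the time mixes observed times with lower bounds. The average then describes the shorter of time to target and follow-up, while the table title promises time to target.

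The direction of the error is awkward. A subject who leaves after Week 2 without reaching target gets the same value, about 15 days, as one who reaches target at Week 2. Early exit may also be linked to poor response: Protocol 12.1(4) allows withdrawal when Hb cannot be controlled in range, and efficacy data stop the day after rescue. Treatment failure can therefore make the drug look faster. A reader who sees a mean with a 95% CI under that title will take it as the average time to target.

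**Working it through.** The plan states no result for this item, and its sample size of 20 rests on feasibility (Protocol 6.1), so there is no figure to reproduce. The check applies the rule literally to assumed data.

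**Inputs from the documents.** Visits fall at Days 14, 28, 42, 56, 70, 84 and, at the end, 168 (Protocol Table 9.1-1, first day = Day 0). With the plus-1 rule these become 15, 29, 43, 57, 71, 85 and 169. N is 20, or fewer after the first-day Hb exclusion; 16 is used as an assumed smaller value.

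**Effect of one early non-reacher.** Shift in the mean = (169 − d)/N, where d is the last evaluation day.

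| d | N=20 | N=16 |
|---|---|---|
| 15 | 154/20 = 7.7 | 154/16 = 9.6 |
| 43 | 126/20 = 6.3 | 126/16 = 7.9 |
| 85 | 84/20 = 4.2 | 84/16 = 5.25 |

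**Worked example (assumed).** Fifteen reachers: two at Day 15, four at 29, four at 43, two at 57, two at 71, one at 85. Their sum is 30 + 116 + 172 + 114 + 142 + 85 = 659, so their own mean is 659/15 = 43.9 (95% CI 32.4–55.5). Five subjects never reach target. Only their last evaluation days vary below; those not listed as leaving complete at Day 169.

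| Non-reachers leaving early | Sum/20 = SAP mean | SD | 95% CI | SAP median | Kaplan-Meier reached by Week 24 |
|---|---|---|---|---|---|
| none | 1504/20 = 75.2 | 58.4 | 47.9–102.5 | 50 | 75.0% |
| Day 15 | 1350/20 = 67.5 | 55.4 | 41.6–93.4 | 43 | 78.8% |
| Days 15, 43 | 1224/20 = 61.2 | 50.2 | 37.7–84.7 | 43 | 82.1% |
| Days 15, 29, 43, 57 | 972/20 = 48.6 | 34.4 | 32.5–64.7 | 43 | 91.8% |
| Days 15, 15, 29, 29, 43 | 790/20 = 39.5 | 20.2 | 30.0–49.0 | 36 | 100% |

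The CI is mean ± t(0.975, 19) × SD/√20. In the first row this is 75.2 ± 2.093 × 58.36/4.472 = 75.2 ± 27.3.

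The first four means span 75.2 − 48.6 = 26.6 days with the same 15 responses. All four exceed the reachers' 43.9; the fifth falls below it. So the distortion has no fixed direction relative to the reachers' mean.

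**Kaplan-Meier with non-reachers censored at the same dates.** The median (first day with survival at or below 0.5) is 43 in every row. In the first row survival is exactly 0.50 at Day 43, so software that averages would print 50. The log-log 95% CI of the median is 29–85 in the first row and 29–71 in the next three.

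**Cumulative proportion.** The last column shows a limit of plain censoring. In the fourth row survival is (18/20)(13/17)(8/12)(5/7)(2/4)(1/2) = 0.082, so 91.8% appear to reach target although 15/20 = 75% did. Holding non-reachers as not reached to Day 169 gives 75.0% in every row.

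**Limiting case.** If none of 20 subjects reached target and they left at Day 15 (5), 29 (10) and 43 (5), the table would still print (75 + 290 + 215)/20 = 29.0 days (95% CI 24.2–33.8).

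**The case against.** The strongest reply is that the rule supplies the censoring time. Last evaluation is the usual censoring date, the Kaplan-Meier plot is ordered in the next sentence, and the SAP is a translation, so its exact phrasing should not bear too much weight. That may well be the intent, and the date is sound for that use. But the rule sits with the descriptive statistics, and nothing takes non-reachers out of them. The public SAP text ends at section 10, apart from the errata, so a note in the figure list or listings cannot be ruled out.

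Second, if every non-reacher completes Week 24, the mean is a time restricted to about Day 169, which can be interpreted if labelled. This is right, but the rule does not require completion and the table carries no such label.

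Third, the large spreads need many early exits. The usual ESA-rescue route requires at least two weeks at maximum dose, and one-tablet increases are in principle at least four weeks apart, so it opens only around Week 8 to 10. Earlier exits need discretionary rescue or withdrawal, which are allowed but of unknown frequency. One early exit moves the mean by at most 7.7 days at N=20, against CI half-widths of about 26 to 27 days in the first two rows. This stands: the four- and five-exit rows are extreme.

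Fourth, SAP 6.3 and 7.5 already cut efficacy data after rescue. That also stands; repeating the cut-off in 7.5.1(4) would only add clarity.

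Finally, visit-by-visit proportions, per-subject Hb plots, and rescue and discontinuation tables show who left. They do not correct the printed mean, SD and CI.

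**Conclusion.** The concern holds. Followed as written, 7.5.1(4) yields a mean, SD and 95% CI that pool observed times with lower bounds, and early failures shorten the mean. The wording alone establishes this. Its size depends on reach and exit patterns that the documents do not give: nil if all eligible subjects reach target, 4.2 to 7.7 days per early-leaving non-reacher at N=20 for exits between Day 85 and Day 15, and tens of days only with several early exits. The SAP median is little affected in the first four rows (50, then 43) but drops to 36 in the fifth.

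Consequences are limited. The item has no test, threshold or comparator, and mean Hb at Weeks 20 and 24 is unaffected. The Kaplan-Meier curve is sound for time to target if non-reachers are censored and exit is unrelated to response. This should be fixed because the item is listed under the primary endpoint and the printed interval invites a wrong reading; it does not threaten the trial's main result.

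**What to change.** In SAP 7.5.1(4):

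- Define the event as the first Hb in the target range. Use the assumed date only to censor subjects who do not reach it, and remove it from the descriptive statistics.
- State that rescued subjects are censored at their last evaluable Hb on or before the rescue day, in line with 6.3 and 7.5.
- Report the number reached out of N, and the Kaplan-Meier median with its 95% CI.
- Label any mean of days as reachers only and print n/N beside it. Such a mean conditions on success and must not stand alone.
- Optionally, add a sensitivity version that keeps subjects rescued, or withdrawn for lack of Hb control, as not reached to Week 24, because censoring them at exit can overstate the cumulative proportion. It needs a stated definition of that group.

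The cost is SAP wording and reprogramming Table 14.2.2.5.1. No new data are needed and clinical conduct does not change. The reported days may move either way.

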### 7.5.2 Analysis of other endpoints

(1) Changes in mean Hb values from the first day of the treatment period at Week 20 and Week 24 of the treatment period

Descriptive statistics for change from Hb value on the first day of the treatment period to mean Hb values at Week 20 and Week 24 in the treatment period should be calculated. A paired t-test should be performed for before and after comparison of changes from the first day of the treatment period. The analysis should be conducted using the MMRM model (with compound symmetry [CS] for a variance-covariance matrix within subjects). LSMeans, its standard errors, and 2-sided 95% CI for change from Hb value on the first day of the treatment period to mean Hb values at Week 20 and Week 24 of the treatment period should be calculated.

(2) Proportion of subjects with a  $\geq 1.0$  g/dL increase in mean Hb values from the first day of the treatment period at each time point of the treatment-period.

The number, proportion, and 95% CI (Clopper-Pearson [exact] method) of the proportion of subjects with a mean Hb increase of  $\geq 1.0$  g/dL from the first day to each evaluation time point of the treatment period should be provided.

(3) Proportion of subjects who received ESA rescue therapy, blood transfusion, or phlebotomy

The number, proportion of subjects and 95% CI (Clopper-Pearson [Exact] method) of the proportion of subjects receiving rescue therapy with an ESA formulation should be provided, after the first day of the treatment period, in each period between scheduled study visits and during the entire treatment period from the first day to Week 24 of the treatment period.

The analyses same to the above subjects receiving rescue therapy with ESA formulation should be performed for subjects receiving rescue therapy with RBC transfusion or receiving phlebotomy.

(4) Study drug dosage

1) Study drug dosage

Descriptive statistics of mean daily dose should be calculated for each scheduled study visit from the first day of the treatment period up to treatment period Week 24. The time course diagram for mean daily dose should be separately prepared. 95% CI of the mean will be represented by an error bar. Each period between scheduled study visits is defined as the period between the scheduled visit and the day before the next scheduled study visit.

2) Distribution of dose of MT-6548 tablets

The number, proportion, and 95% CI (Clopper-Pearson [Exact] method) of the proportion of subjects per daily dose based on the prescription should be provided at each evaluation time point.

The proportion of subjects per daily dose based on the prescription at each evaluation time point of the treatment period should be provided as a stacked bar graph with the number of subjects in each treatment group as 100%. Stacked bar charts should be separately prepared.

If no prescription is available on the day of each evaluation timepoint of the treatment period, the dose should be based on the immediately before prescription.

(5) Total number of dosage adjustments

The cumulative total number of dose adjustments from the first day of the treatment period to Week 24 of the treatment period should be calculated, and the number, proportion, and 95% CI (Clopper-Pearson [Exact] method) of the proportion of subjects are shown. The number and proportion of subjects by total number of dose adjustments for each scheduled study visit period should be shown. The number, proportion, and the 95% CI (Clopper-Pearson [Exact] method) of the proportion of subjects should be provided for subjects defined below in each period between scheduled study visits and during the entire period from the first day to Week 24 of the treatment period. If a subject is included in more than one definition, the subject should be counted in each definition.

✓ No dose adjustment: No change

With dose adjustment: Dose adjustment, dose increase (Increase), dose decrease (Decrease), drug interruption (Interrupt)

Dose adjustment should include the number of times of increase, decrease, and interruption, and should not count as the increase when it is resumed after interruption.

(6) Iron supplement dosage

The following should be provided according to the 3 categories of oral iron supplement, intravenous iron supplement, and iron supplement (any route).

Descriptive statistics of the mean dose of iron supplement per month should be calculated for the screening period, and after the first day of the treatment period, in each period between scheduled study visits and during the entire treatment period from the first day to Week 24 of the treatment period.

Descriptive statistics of the change in the mean dose of iron supplement per month from the baseline (mean dose of iron during the screening period) should be calculated, after the first day of the treatment period, in each period between scheduled study visits and during the entire treatment period from the first day to Week 24 of the treatment period. Before and after comparison should be conducted for changes from baseline using the paired t-test. Descriptive statistics should be calculated for the changes.

The dosage of iron supplement should be calculated using the dose as iron.

If no iron supplement is administered, the dose should be tabulated as 0 mg. Subjects who changed the administration route of an iron supplement during the treatment period and subjects who had never received an iron supplement during the treatment period should be excluded from the tabulation.

(7) Proportion of subjects receiving oral, intravenous, or iron supplement (any route)

The number, proportion, and 95% CI (Clopper-Pearson [Exact] method) of the proportion of subjects treated with iron supplement via oral, intravenous, or any route should be provided for screening period, and after the first day of the treatment period, in each period between scheduled study visits and during the entire treatment period from the first day to Week 24 of the treatment period. Before and after comparison should be conducted for changes between baseline (proportion of subjects receiving iron supplements by the aforementioned route in screening period) and each period between scheduled study visits using the McNemar test.

Subjects who have not received an iron supplement are to be subjects who have never received an iron supplement during the relevant period, and subjects who have received iron supplement via oral, intravenous, or any route are to be subjects who have received an iron supplement at least once during the relevant period.

(8) Proportion of subjects with serum ferritin  $\geq 100$  ng/mL or TSAT  $\geq 20\%$ .

The number, proportion, and 95% CI (Clopper-Pearson [exact] method) of the proportion of subjects with serum ferritin levels of  $\geq 100$  ng/mL or TSAT levels of  $\geq 20\%$  should be provided at each evaluation time point of the treatment period. Before and after comparison should be conducted for changes between baseline and each period between scheduled study visits using the McNemar test.

(9) Changes and rate of changes in iron-related indices (serum iron, TIBC, TSAT, and serum ferritin levels) and hepcidin from the first day of the treatment period

Descriptive statistics should be prepared for measured values of iron-related measures (serum iron, TIBC, TSAT, and serum ferritin) and hepcidin at each evaluation time point of the treatment period and their change and change rates from the first day of the treatment period. A paired t-test should be performed for before and after comparison of changes and change rates from the first day of the treatment period.

LSMean, its standard errors, and 2-sided 95% CI should be calculated for the change in iron-related measures (serum iron, TIBC, TSAT, and serum ferritin) and hepcidin from the first day of the treatment period to each evaluation time point using the MMRM model (with compound symmetry [CS] for a variance-covariance matrix within subjects). Only the serum ferritin value at each evaluation time point of the treatment period should be analyzed similarly.

The time course diagram of changes in the iron-related measures (serum iron, TIBC, TSAT, and serum ferritin levels) and hepcidin from the first day of the treatment period to each evaluation time point should be prepared. The 95% CI of LSMean will be represented by an error bar. For only the serum ferritin value, a time course diagram should also be prepared for mean ferritin value at each evaluation time point of the treatment period. 95% CI of the mean will be represented by an error bar.

The serum ferritin values are shown as follows.

- The following scatter plot chart should be provided by treatment group. Linear regression should be performed to calculate the p-value and correlation coefficient of the test with zero slope as the null hypothesis.

x: Serum ferritin values at baseline

y: Serum ferritin values at Week 24 of the treatment period

- (10) Changes in hematocrit, red blood cell count, reticulocyte (count and rate), mean corpuscular volume, mean corpuscular hemoglobin, and EPO from the first day of the treatment period

Descriptive statistics of hematocrit, red blood cell count, reticulocyte (number and rate), mean corpuscular volume, mean corpuscular hemoglobin, and EPO should be calculated at each evaluation time point. And, the change from the first day of the treatment period should be obtained, and the descriptive statistics should be calculated. A paired t-test should be performed for before and after comparison of changes from the first day of the treatment period.

LSMean, its standard errors, and 2-sided 95% CI should be calculated for the change in hematocrit, red blood cell count, reticulocyte (number and rate), mean corpuscular volume, mean corpuscular hemoglobin, and EPO from the first day of the treatment period to each evaluation time point using the MMRM model (with compound symmetry [CS] for a variance-covariance matrix within subjects).

A histogram of EPO measurements should be prepared for evaluation time point at Week 24 of the treatment period.

- (11) Changes in systolic blood pressure, diastolic blood pressure, and blood glucose from the first day of the treatment period, changes and the rate of change in lipid (total cholesterol, LDL-C, HDL-C, LDL-C/HDL-C ratio, triglycerides) from the first day of the treatment period

Systolic blood pressure, diastolic blood pressure, lipids (total cholesterol, LDL-C, HDL-C, LDL-C/HDL-C ratio, triglycerides), and blood glucose should be analyzed in the same manner as hematocrit, red blood cell count, and reticulocyte (count and rate) in the preceding section.

The change from the first day of the treatment period should be obtained, and the descriptive statistics should be calculated. A paired t-test should be performed for before and after comparison of changes from the first day of the treatment period. LSMean, standard error, and 2-sided 95% CI should be calculated for the change from the first day of the treatment period using the MMRM model (with compound symmetry [CS] for a variance-covariance matrix within subjects).

The descriptive statistics should be similarly calculated for the change rate from the first day of the treatment period at each evaluation time point of the lipid (total cholesterol, LDL-C, HDL-C, LDL-C/HDL-C ratio, triglycerides), and LSMean, standard error, and 2-sided 95% CI should be calculated using the MMRM model (with compound symmetry [CS] for a variance-covariance matrix within subjects).

- (12) QOL indices (EQ-5D-5L, KDQOL)

1) EQ-5D-5L

The number, proportion, and 2-sided 95% CI (Clopper-Pearson [Exact] method) of the proportion of subjects in responses in 5 levels to the 5 questions (mobility, self care, usual activities, pain/discomfort, anxiety/depression) should be provided at each evaluation time point.

For Index value and VAS score, descriptive statistics of measured values and descriptive statistics of changes from the first day of the treatment period should be provided at each evaluation time point. A paired t-test should be performed for before and after comparison of changes from the first day of the treatment period.

The change in Index value and VAS score from the first day of the treatment period at each evaluation time point should be compared between groups using the MMRM model (with compound symmetry [CS] for a covariance matrix within subject variance), and LSMean, its standard errors, and 2-sided 95% CI should be calculated.

2) KDQOL

Descriptive statistics of KDQOL should be calculated by subscale (Section 4 [Table 4.16.2] “subscale”) for measured values and changes from the first day of the treatment period at each evaluation time point. Scores by subscale should be calculated using a scoring method (Section 4.16).

A paired t-test should be performed for before and after comparison of changes in KDQOL from the first day of the treatment period.

LSMean, its standard errors, and 2-sided 95% CI should be calculated for the change in KDQOL from the first day of the treatment period to each evaluation time point using the MMRM model (with compound symmetry [CS] for a variance-covariance matrix within subjects).

